3. DESCRIPTION OF RESEARCH PROTOCOL

A. Study Design – Overview, Methods, Procedures

Overall study design:

Patients diagnosed with chronic migraine (fulfill criteria for CM as defined in the ICHD-3 beta), especially those complaining about chronic muscle tenderness, are routinely considered good candidate to benefit from a surgery in which trapped nerves are decompressed. In routine clinical care, such patients are referred to [name] (plastic surgeon performing these procedures) to determine whether or not they fit to undergo the nerve decompression procedure. Of great importance to the evaluation of the proposed study is the fact that the decision on whether or not to operate is unrelated to and independent of any academic study. Those deemed good candidate for the surgery, which include fulfilling all inclusion/exclusion criteria, would be presented with an option to hear about the study from a research nurse. Those interested in hearing about the study will be presented with all the necessary details required and then given the option to sign (or not to sign). They will be given as much time as needed to sign the consent form and have the option to take the consent form home and call in interested.

Since the surgery itself is unrelated to the proposed study, all patients (those who sign the informed consent and those who chose not take part in the study) are booked for the surgery. Usual waiting time is 3-6 month.

Those who agree to participate in the study, will be asked to fill out a 15min headache questionnaire that contains questions about their headaches. Subjects will also be asked to complete a headache diary 3 months prior to botox injections.

Enrolled subjects will be booked for another visit to [name] clinic 30 days prior to their planned surgery. In this visit, they will be injected with 40 units of Botox in one side of their head/neck as detailed below.

During surgery, calvarial periosteum, pericranial muscles and fascia surrounding nerves that are routinely removed and discarded, will be collected by [name], stored in in RNAlater Solution, Ambion, CA, de-identified, frozen, and shipped overnight to [name] lab at BIDMC, where each sample will be recorded, verified, prepared for processing, and analyzed for targeted transcriptome and epigenome involved in inflammatory and immune responses.

Clinical Site Study Procedures

The following research study activities will take place exclusively at MGH:

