Those who agree to participate in the study, will be asked to fill out a 15min headache questionnaire that contains questions about their headaches. Subjects will also be asked to complete a headache diary 3 months prior to botox injections.

The headache diary will be filled out every day for 3 months prospectively prior to botox injection. Subjects will indicate whether they had migraines that day (check date box), what severity the migraines were (on a scale of 0-10), what the duration was (hours), what the location was, which other symptoms they experienced, which medications they took, how often they went to the ED, saw doctors or missed work and how much the total cost was. The total time spent every day filling out the diary should not exceed 5min.

Enrolled subjects will be injected with Botox on one side of the back of the head. The FDA-approved injection paradigm includes 7 muscles (Frontalis, Corrugator, Procerus, Occipitalis, temporalis, Trapezius, and the Cervical Paraspinal muscle group), 31 sites and 155 units divided as follows: Frontalis – 4 sites, 5 units in each; Corrugator – 2 sites, 5 units in each; Procerus – 1 site, 5 units; Occipitalis – 6 sites, 5 units at each; Temporalis – 8 sites, 5 units in each; Trapezius – 6 sites, 5 units at each; Cervical

Paraspinal – 4 sites, 5 units in each.

Of these muscles, sites and doses, patients will be injected (from a 100 Unit vial of OnabotulinumtoxinA reconstituted per product manufacturer label instructions) as follows:

- (A) 2 sites in the Occipitalis muscle (5 units each)
- (B) 4 sites in the Cervical Paraspinal muscle group (5 units each)
- (C) 2 sites in the Trapezius muscle (5 units each)

These injections will be given into one side only. This deviates from the standard of care, as Botox is usually injected on both sides if pain is experienced on both sides. The selection will be random based on subject number. Odd numbers will be injected on the right and even numbers on the left.

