Thirty days later, patients will undergo a study-unrelated nerve decompression surgery. This procedure involves the removal of different tissues surrounding trapped branches of the occipital nerve. These tissues include muscles, fascia, and periosteum (discarded tissue). The amount of tissue removed at each area is many folds larger than the amount of tissue needed for sampling (less than the size of 1 grain of rice).

From the time of informed consent and for 3 months following injection, all self-reported adverse events will be reviewed by the study physician at each patient contact (patients are followed every 4 weeks after botox injection and one week, one month, three months, one year and after that yearly after surgery). All serious adverse events will be reported to the IRB and designated safety monitor within 24 hours of awareness of the event.

There will be two visits:

Screening visit: Patients will be screened for eligibility. This will be performed during the regular clinical assessment for surgery. The study visit will take 30min. The subject will be asked to complete

a 15 min questionnaire and will be asked to fill out a 3m headache diary which may take up to 5min a day.

Preoperative visit: will be injected with Botulinum Toxin. This will take 30 minutes.

There will be further routine clinical visits postoperatively (one week, 3 months and 12 months). However, these visits are not related to the study but are part of regular follow up. No study materials for this study will be collected as part of this visit.

[figure not shown]
Analysis to be Done at BIDMC

- (A) Tissue processing, RNA isolation, genetic processing and mRNA counting will occur in [name] lab at Beth Israel Deaconess Medical Center, Harvard Medical School.
- (B) Bioinformatics and biostatistics analyses will be conducted at [name] lab at Beth Israel Deaconess Medical Center, Harvard Medical School.

B. Statistical Considerations

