- Patient is capable and willing to provide informed consent
- Female subjects of child bearing potential must have a negative pregnancy test at enrollment and agree to remain abstinent or use acceptable methods of birth control (i.e., hormonal contraceptives, intrauterine device, diaphragm with spermicide, cervical cap or sponge, condoms or partner has had a vasectomy) for three months following injections of Botox
- Patients referred by their primary Neurologist to the study surgeon and who are determined to be candidates for surgical decompression of extracranial sensory nerves.
- Patient agrees to abstain from protocol-specific excluded medications (see Appendix A) beginning 14 days prior to the decompression surgery.

Exclusion Criteria:

- Patient has hypersensitivity reactions or other intolerance to Botox
- Patient is pregnant or trying to become pregnant with the timeframe of the study.
- Infection at proposed injection sites

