- Swelling of the eyelid
- Dryness of the eye
- Irritation/tearing of the eye
- Difficulty in closing the upper lid
- Sensitivity to light
- Double vision
- Soreness and/or bruising at the injection sites
- Skin rash
- Loss of facial wrinkling
- Localized muscle weakness in the muscles which have been injected
- Slight weakness in other muscles in the neck
- Difficulty swallowing
- Generalized weakness and fatigue

C. If you experience any illness or discomfort during the study, you should notify [name]. [name] will then evaluate you to determine if you should continue in the study.

D. There may be side effects or discomforts from the study treatment which are not yet known. You could have an allergic reaction to **BOTOX**. A severe allergic reaction could be life-threatening.

E. Women who are pregnant, nursing a child, or planning a pregnancy during this study period may not participate in this study. You must confirm that, to the best of your knowledge, you are not now pregnant, and that you do not intend to become pregnant during the study. Prior to entering the study, you and the study doctor must agree on the method of birth control you will use during the study. If you suspect that you have become pregnant during the study, you must notify the study doctor immediately. The sponsor of the study may need access to your medical records regarding your pregnancy and the outcome of your pregnancy. In addition, if you are pregnant or become pregnant during the study, there may be a risk of miscarriage or fetal malformation.

F. Treatment with **BOTOX** for the treatment of migraine headaches may result in the formation of antibodies that may reduce the effectiveness of subsequent treatments with **BOTOX** for other purposes.

G. Botox injections are associated with pain from the needle prick with pain from the needle prick. A bruise may develop at the site, and there is a small chance you might get an infection.

Overall, we believe the risks of this study are sufficiently low and that the benefits of information to be gained and the potential benefit of improved migraine treatment outweigh the risks in this study.

Unanticipated problems involving risks to subjects or others including adverse events will be reported to the PHRC in accordance with PHRC unanticipated problems reporting guidelines.

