Since the surgery, itself is unrelated to the proposed study, all patients (those who sign the informed consent and those who chose not take part in the study) are booked for the surgery. Usual waiting time is 3-6 month. Those who signed the informed consent will be booked for another visit to [name] clinic 30 days prior to their planned surgery. In this visit, they will be injected with 40 units of Botox in one side of their head/neck as detailed below.

During surgery, calvarial periosteum, pericranial muscles and fascia surrounding nerves that are routinely removed and discarded, will be collected by [name], stored in in RNAlater Solution, Ambion, CA, de-identified, frozen, and shipped overnight to [name] lab at BIDMC, where each sample will be recorded, verified, prepared for processing, and analyzed for targeted transcriptome and epigenome involved in inflammatory and immune responses.

The current standard of care for screening for migraine surgery includes injection of Botox to identify nerve triggers. In the occipital region, botox is either injected unilaterally or bilaterally depending on where pain occurs. When pain occurs bilaterally, Botox is injected on both sides. Subjects included in this study have bilateral occipital pain and would therefore as part of routine standard care be injected on both sides. As per this protocol, subjects will only be injected on one side. The risks of unilateral injection of botox (in addition to the risk of Botox in general outlined by the FDA) include continued pain on the uninjected side and/or injected side and one- sided muscle weakness, one- sided bruising, one sided infection on the injected side. . More generally, botox injections may cause the formation of anti-botox antibodies, which may decrease the effectiveness of botox treatment in other areas.

Subjects will be informed that they have the option to be injected with Botox on the uninjected side if any unwanted symptoms are experienced on the uninjected side. The cost of injection on the other side will be covered by the study funds.

A separate IRB protocol has already been approved for the use of discarded tissues, therefore this is also standard procedure.

Describe how risks to subjects are minimized, for example, by using procedures which are consistent with sound research design and which do not unnecessarily expose subjects to risk or by using procedures already being performed on the subject for diagnostic or treatment purposes.

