- Irritation/tearing of the eye
- Difficulty in closing the upper lid
- Sensitivity to light
- Double vision
- Soreness and/or bruising at the injection sites
- Skin rash
- Loss of facial wrinkling
- Localized muscle weakness in the muscles which have been injected
- Slight weakness in other muscles in the neck
- Difficulty swallowing
- Generalized weakness and fatigue

C. If the subject experiences any illness or discomfort during the study, they should notify [name]. [name] will then evaluate the subject to determine if the subject should continue in the study.

D. There may be side effects or discomforts from the study treatment which are not yet known. The subject could have an allergic reaction to BOTOX. A severe allergic reaction could be life-threatening.

E. Women who are pregnant, nursing a child, or planning a pregnancy during this study period may not participate in this study. The subject must confirm that, to the best of their knowledge, they are not now pregnant, and that they do not intend to become pregnant during the study. Prior to entering the study, the subject and the study doctor must agree on the method of birth control that they will use during the study. If the subject suspects that they have become pregnant during the study, they must notify the study doctor immediately. The sponsor of the study may need access to the subject's medical records regarding their pregnancy and the outcome of their pregnancy. In

addition, if they are pregnant or become pregnant during the study, there may be a risk of miscarriage or fetal malformation.

F. Treatment with BOTOX for the treatment of migraine headaches may result in the formation of antibodies that may reduce the effectiveness of subsequent treatments with BOTOX for other purposes.

G. Botox injections are associated with pain from the needle prick with pain from the needle prick. A bruise may develop at the site, and there is a small chance the subject might get an infection.

Overall, we believe the risks of this study are sufficiently low and that the benefits of information to be gained and the potential benefit of improved migraine treatment outweigh the risks in this study.

EXPECTED BENEFITS

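### The only pregnancy test in the visible text is at enrolment, months before the injection visit; a test before dosing would be a cheap safety improvement

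*Combined protocol and SAP*

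**What the plan says.** The combined protocol and SAP sets the test in section 3.C, Inclusion Criteria: "Female subjects of child bearing potential must have a negative pregnancy test at enrollment". The same criterion asks for abstinence or contraception, and the period it names is the three months after injection. The Protocol Summary at the end of the document repeats the criterion. The exclusion criteria in both places add: "Patient is pregnant or trying to become pregnant with the timeframe of the study".

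Dosing comes later. Section 3.A says "Enrolled subjects will be booked for another visit", scheduled 30 days before surgery, at which Botox is given. The Protocol Summary puts it this way: "Those who signed the informed consent will be booked for another visit". Between the two visits there is a diary: "The headache diary will be filled out every day for 3 months prospectively prior to botox injection". The list of two visits in section 3.A describes the second one only as "Preoperative visit: will be injected with Botulinum Toxin. This will take 30 minutes", and the Protocol Summary does the same.

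Other safeguards appear elsewhere. Item E of section 5, and item E under Foreseeable Risks in the Protocol Summary, require a method of birth control to be agreed before entry for use during the study, and require a suspected pregnancy to be reported at once. Both items warn of harm; section 5 says "if you are pregnant or become pregnant during the study, there may be a risk of miscarriage or fetal malformation". Under Equitable Selection, the Protocol Summary says that pregnant women are not candidates for the surgery and that Botox is not recommended in pregnancy.

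**The concern.** The pregnancy exclusion protects a fetus from exposure to the study drug, so it matters on the day of injection. The listed test checks it at the start of a diary period that the plan itself places before dosing. A woman who tests negative at enrolment and conceives during that period could be injected with every written step followed, provided she does not suspect the pregnancy.

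Patient safety is what is at stake. There is also a small practical cost: by the protocol's own account, a pregnancy discovered after injection would rule out the surgery. The subject would then have been exposed for the study without yielding any tissue.

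**Working it through.** The plan states no figure for the interval between test and dose, so there is none to reproduce. The interval follows from the schedule by two routes.

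**Inputs**
- Pregnancy test: one, at enrolment (section 3.C; Protocol Summary).
- Diary: daily for 3 months, prospective, before injection, kept by people who have already agreed to take part (section 3.A; Protocol Summary).
- Usual wait for surgery: 3 to 6 months (section 3.A; Protocol Summary).
- Injection: 30 days before surgery (same places).
- Recruitment ceiling: 65 (section 3.C; Protocol Summary).

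**Assumption.** Enrolment has no exact date in the plan. I take it as the time of consent, with the diary starting then or later and the wait for surgery counted from then.

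**Route 1, diary.** 3 × 365.25/12 = 91.3 days. If the diary is completed as written, the test is about 3 months old or more at dosing.

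**Route 2, surgical wait.** 3 months less 30 days: 91.3 − 30 = 61.3 days. 6 months less 30 days: 182.6 − 30 = 152.6 days. The test is about 61 to 153 days old, that is, about 2 to 5 months.

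**Reconciling the two.** A full diary needs a wait of at least 91.3 + 30 = 121.3 days, or about 4 months. For waits of 4 to 6 months both routes hold and the interval is about 3 to 5 months. For a wait of 3 to 4 months either the diary is cut short or the surgery date moves; the text does not say which.

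**What covers the interval**

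| Safeguard | Covers the time between test and dose? | Detects an unsuspected pregnancy? |
|---|---|---|
| Enrolment test | No, it precedes it | No |
| Contraception in the inclusion criterion | Not named; the stated period follows injection | No |
| Contraception agreed under item E | Yes | No |
| Duty to report a suspected pregnancy | Yes | No |
| Pregnancy bars surgery | Yes, for a known pregnancy | No |

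Tests listed between enrolment and injection, or on the injection day: 0. Tests added by the fix: at most 65, if every recruit were a woman of childbearing potential.

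**The case against.** The strongest objection is that the visit list proves little by its silence. The screening visit in the same list mentions no pregnancy test either, although the inclusion criterion requires one at enrolment. These short descriptions are plainly not complete lists of procedures. In addition, a figure beside the list in section 3.A is not shown and the consent pages were removed. A reader might infer that no test will be done before dosing. The documents do not support that. They support only the statement that none is listed in the visible text.

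A reader might also infer that the gap is never shorter than 3 months. That holds only if the diary is completed, and nothing in the text makes an incomplete diary a bar to injection. The usual surgical wait alone allows about 2 months.

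A third tempting reading is that contraception lapses before dosing, because the inclusion criterion names only the time after injection. Item E closes that gap by requiring contraception throughout the study.

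The stakes are also low. Treatment is a single session of 2×5 + 4×5 + 2×5 = 40 Units by the schedule in section 3.A, the attached label does not list pregnancy as a contraindication, and routine care would inject these patients on both sides. Women booked for surgery 30 days later are unlikely to be knowingly pregnant. All of this stands and limits the weight of the point. It does not supply a check for a pregnancy the subject is unaware of. Nor should the label's animal data be turned into a fixed safety margin for the study dose, because the no-effect levels in label section 8.1 differ by dosing schedule.

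**Conclusion.** The point holds as a minor patient-safety improvement. As visibly written, the plan verifies pregnancy status once, about 3 months before dosing if the diary is completed, or about 2 to 5 months before by the usual surgical wait. After that it relies on contraception, self-report and surgical candidacy. This rests on the visible text and on taking enrolment as the time of consent.

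The documents give neither the number of women of childbearing potential nor an expected pregnancy rate, so the number affected cannot be estimated; it is likely to be small. A reader might take this for an error in the plan or a breach of its own rules. It is neither: the protocol sets an exclusion, backs it with real safeguards, and leaves out one inexpensive confirmation at the time it matters most. Sample size, power and analysis are unaffected.

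**What to change.** Keep the enrolment test, which the inclusion criterion requires and which avoids asking an ineligible woman to keep a diary for 3 months. Add to the preoperative visit, in section 3.A and in the matching list in the Protocol Summary: *Subjects of childbearing potential have a urine pregnancy test before dosing; a subject with a positive test is not injected and leaves the study.*

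The time from last test to dose then falls from months to about zero. The cost is at most 65 urine tests at an existing 30-minute visit, one sentence in two places, and probably a consent revision. The documents give no unit price; that the test is inexpensive is a judgement. A very early pregnancy could still be missed, so the contraception and reporting duties should stay as they are.

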4. POSSIBLE BENEFITS

It is not possible to predict whether participants will benefit directly from participation in this study. However, their participation may help others in the future as a result of knowledge gained from the research

It is important to note that the clinical outcome of the procedure is unrelated to the proposed study. While improvement (or lack of improvement) in headache days per month after the procedure is followed by [name], it is outside the scope of the proposed study and as such will not be collected and/or reported.

5. POSSIBLE RISKS AND ANALYSIS OF RISK/BENEFIT RATIO

Only subjects who have been selected as a surgical candidate for sensory nerve decompression of chronic headache would have their tissue tested. The taking of the periosteal sample would add no additional risk to the operation, as we are obtaining tissue *discarded* during surgery.

Botox therapy is currently approved by the FDA for preventive treatment of migraines.

All the potential risks of Botox injections as issued by the FDA are as follows. As we are only injecting the back of the occiput, symptoms occurring around the eyes, the oropharynx or generalized symptoms are very unlikely.

A. General:

- There have been rare spontaneous reports of death, sometimes associated with dysphagia, pneumonia, and/or other significant debility, after treatment with botulinum toxin.
- *There have also been rare reports of adverse events involving the cardiovascular system, including arrhythmia and myocardial infarction, some with fatal outcomes. Some of these patients had risk factors including cardiovascular disease. The exact relationship of these events to the botulinum toxin injection has not been established.*

- The following events have been reported since the drug has been marketed and a causal relationship to the botulinum toxin injected is unknown: skin rash (including erythema multiforme, urticaria and psoriasisiform eruption), pruritus, and allergic reaction.
- In general, adverse events occur within the first week following injection of **BOTOX®** and while generally transient may have a duration of several months. Localized pain, tenderness and/or bruising may be associated with the injection. Local weakness of the injected muscle(s) represents the expected pharmacological action of botulinum toxin. However, weakness of adjacent muscles may also occur due to spread of toxin.
- Extraocular muscles adjacent to the injection site can be affected, causing ptosis or vertical deviation, especially with higher doses of **BOTOX**. The incidence rates of these adverse effects in 2058 adults who received a total of 3650 injections for horizontal strabismus are 15.7% and 16.9%, respectively.
- The incidence of ptosis was 0.9% after inferior rectus injection and 37.7% after superior rectus injection.

B. Side effects and discomforts associated with study treatment that you may experience include the following and some of these effects may last as long as 3 to 4 months:

- Drooping of the upper lid
- Swelling of the eyelid
- Dryness of the eye
- Irritation/tearing of the eye
- Difficulty in closing the upper lid
- Sensitivity to light
- Double vision
- Soreness and/or bruising at the injection sites
- Skin rash
- Loss of facial wrinkling
- Localized muscle weakness in the muscles which have been injected
- Slight weakness in other muscles in the neck
- Difficulty swallowing
- Generalized weakness and fatigue

C. If you experience any illness or discomfort during the study, you should notify [name]. [name] will then evaluate you to determine if you should continue in the study.

D. There may be side effects or discomforts from the study treatment which are not yet known. You could have an allergic reaction to **BOTOX**. A severe allergic reaction could be life-threatening.

E. Women who are pregnant, nursing a child, or planning a pregnancy during this study period may not participate in this study. You must confirm that, to the best of your knowledge, you are not now pregnant, and that you do not intend to become pregnant during the study. Prior to entering the study, you and the study doctor must agree on the method of birth control you will use during the study. If you suspect that you have become pregnant during the study, you must notify the study doctor immediately. The sponsor of the study may need access to your medical records regarding your pregnancy and the outcome of your pregnancy. In addition, if you are pregnant or become pregnant during the study, there may be a risk of miscarriage or fetal malformation.

F. Treatment with **BOTOX** for the treatment of migraine headaches may result in the formation of antibodies that may reduce the effectiveness of subsequent treatments with **BOTOX** for other purposes.

G. Botox injections are associated with pain from the needle prick with pain from the needle prick. A bruise may develop at the site, and there is a small chance you might get an infection.

Overall, we believe the risks of this study are sufficiently low and that the benefits of information to be gained and the potential benefit of improved migraine treatment outweigh the risks in this study.

Unanticipated problems involving risks to subjects or others including adverse events will be reported to the PHRC in accordance with PHRC unanticipated problems reporting guidelines.

